## Section 7.0 Study Parameters

### 7.1 Laboratory/imaging Studies:

Parameter	Baseline	Pre- and post-SRT therapy	Post-Treatment Follow-up
History	X	X b	a
Physical examination	X	X b	a
Weight	X	X	a
Vital signs	X	X	a
Performance status (Karnofsky)	X	X	a
CBC, differential, platelet count	X	X Post- SRT	a
Comprehensive metabolic panel (including bilirubin, alk phos, AST, ALT, )	X	X Post- SRT	a

Fill out pain assessment card	X	X Post-SRT	a
AFP	X	X post-SRT	a
PT, PTT, INR	X	X Post-SRT	a
CT	X	X simulation	
MRI	X	X Post-SRT	a
Serum pregnancy test	prn		

*a - will be done at one month and 3 months after the completion of SRT*

*b – A brief physical exam and history will be performed*

#### 7.2 Monitoring of peri- and post-marker implantation morbidity

The liver marker position and geometry will be documented on simulation CT images. Information regarding the development of infectious complications, bleeding, and any implantation associated adverse events will be recorded.

### Section 8.0 Drug Formulation and Procurement

No drugs are used in this study.

### Section 9.0 Toxicity Reporting Guidelines

#### 9.1 Adverse Events that will be reported to UNMC's IRB

9.1.1 Unexpected serious adverse events

9.1.2 Any death, which occurs while the subject is being treated on protocol or occurs within 30 days of completing research related interventions

9.1.3 Toxic deaths will be reported to the UNMC IRB within 24 hours following PI knowledge of the event via e-mail notification to [[contact]](mailto:[contact])

The IRB only requires submission of internal AE reports when the event is unexpected. Internal adverse events occurring on a study which satisfy this criterion must be submitted to the IRB within two business days following the time it becomes known. Any death must be reported immediately. One original of the Internal AE Report form (or Internal Fatal Event form), and one copy of the current IRB approved consent form must be submitted, along with any other relevant information, to the IRB:

The contact information is: Institutional Review Board, University of Nebraska Medical Center, [name]; [contact]; [contact]; e-mail: [[contact]](mailto:[contact])

## 9.2 Reporting of Adverse Events to the Scientific Review Committee of the UNMC Eppley Cancer Center

The SRC defines an adverse event as any undesirable experience associated with the use of the protocol treatment in a patient. The event is considered to be SERIOUS and should be reported when the patient outcome is:

- 9.2.1 Death: Report if the patient's death is suspected as being a direct outcome of the adverse event.
- 9.2.2 Life-threatening: Report if the patient was at substantial risk of dying at the time of the adverse event or it is suspected that the use of the SRT would result in the patient's death.
- 9.2.3 Hospitalization (initial or prolonged): Report if the patient requires admission to the hospital for 24 hours or more or prolongation of a hospital stay results because of the adverse event.
- 9.2.4 Disability. Report if the adverse event resulted in a significant, persistent, or permanent change, impairment, damage or disruption in the patient's body function/structure, physical activities or quality of life.
- 9.2.5 Requires intervention to prevent permanent impairment or damage. Report if you suspect that the use of the protocol treatment may result in a condition which required medical or surgical intervention to preclude permanent impairment or damage to a patient.

Copies of the adverse event report will be submitted to the IRB (when required), to the UNMC Eppley Cancer Data and Safety Monitoring Committee (DSMC).

## 9.3 Data and Safety Monitoring Plan

This protocol will comply with monitoring and adverse event reporting requirements of the UNMC/Eppley Cancer Center Data Monitoring Plan. All research data will be stored in the case report forms in a locked file cabinet. These forms are available only to the investigators, his/her designee (i.e., the study coordinator), the UNMC Eppley Cancer Center Scientific Review Committee (SRC), and representatives of the Institutional Review Board at the University of Nebraska Medical Center. Any information obtained during this study which could identify the subject will be kept strictly confidential and will be identified by code numbers rather than the patient's name. The data safety plan also includes: Weekly review of all patients on study by the investigators. All adverse events will be reported to the PRMS Internal Audit Committee for audit by a clinician not involved with the clinical trial.

All patients will be closely followed for toxicity. Toxicity will be assessed using the revised NCI Common Toxicity Criteria (version 3.0) retrieved from the National Cancer Institute, Cancer Therapy Evaluation Program web site: ([ctepcancer.gov/forms/CTCAEv3.pdf](http://ctepcancer.gov/forms/CTCAEv3.pdf)). Therapy will be discontinued at any time due to the development of unacceptable toxicity. If a Grade 1 or 2 or 3 toxicity develops, the investigator may elect to continue the treatment with careful monitoring. Any grade 4 or greater toxicity according to CTCAE v3 will constitute a DLT. 1) SRT dose escalation will be stopped if 2 patients at a given dose level experience a DLT. If one patient has a DLT, then an additional five patients will be evaluated at the same dose level. 2) Implantation of a liver marker will be stopped if 2 patients experience implant-related-adverse events which do not response to medical or surgical management.

Therapy will be discontinued at any time due to the development of unacceptable toxicity. If, at any time, the data suggest a significant hazard to further dose escalation, regardless of whether the formal stopping rules are satisfied, dose escalation will be halted pending a review of all data. There will be a four week waiting period after the last patient in each cohort completes radiation therapy for toxicity evaluation between dose levels.

Adverse events will be assessed by reports from patients of any adverse events to their physician-investigators and by physical examinations. The following information will be recorded for all adverse events: date of onset, date of resolution, severity, action taken, relationship to study medication and patient outcome. The worsening of a concurrent disease or the development of a new concurrent disease will be regarded as an adverse event and information regarding the event will be added to the adverse event page of the case record book.

The plan also includes the following: the status of all patients participating in this protocol will be reviewed by the principal investigator with the research nurse on the weekly visit during the SRT and on each follow-up visit. During this meeting, the clinical toxicities experienced by the patients will be discussed, and plans will be made for any modification, and whether any changes need to be made to the protocol through an amendment. Any logistical or social issues for the patients will also be addressed at this meeting. The research nurse will be in contact with each patient by either telephone or e-mail. Laboratory studies done at outside facilities are faxed to the research nurse on a real-time basis. Any abnormalities are brought to the attention of the principal investigator or designee.

Patients may continue on concurrent medications for symptom relief on an as needed basis. The need for additional or more potent concurrent medication after the start of the study may constitute an adverse event, and information regarding such an experience will be added to the appropriate page of the case record form. The details of all concurrent medications, including vitamins, blood and blood products, will be recorded on the case record forms.

## Section 10.0 Statistical considerations

### 10.1 Trial Design

This phase I trial will determine safety, dose-limiting toxicities (DLT) and maximum tolerable dose (MTD) of SRT for HCC. Although unacceptable toxicity is unlikely, four dose levels (40, 50, 60, 70 Gy in 5 fractions) will be evaluated in a cohort escalation design of 3-6 patients. At the MTD, 10 additional patients will be enrolled to generate pilot data on radiologic response and to evaluate further toxicity. Patients will start at dose level II (50 Gy at 5 fractions).

#### Endpoints

Toxicity will be graded by NCI Common Toxicity Criteria (CTC Version 3.0). Due to delayed toxicities attributable to radiotherapy, all toxicities observed within 1 month after SRT will be scored. DLT is defined as any of following toxicities, that is possibly, probably or definitely related to SRT occurring within 30 days from the start of treatment:

- a) grade 4 or 5 hepatic
- b) grade 4 or 5 gastrointestinal
- c) grade 4 or 5 thrombocytopenia
- d) grade 4 hepatic liver enzyme elevations persisting for  $\geq 5$  days
- e) any adverse event requiring interruption of therapy by  $\geq 2$  weeks (14 calendar days). This does not include patient desire to discontinue therapy. It does include failure for thrombocytopenia to improve to a level of 80 requiring interruption of therapy.
- f) Any grade 5 treatment-related adverse event

The MTD of SRT is defined as the highest dose level at which no greater than 2 DLT is observed in 6 patients.

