### **Evaluation:**

- 1) Liver, right kidney and small bowel toxicity will be evaluated according to CTCAEv3.0
- 2) Tumor response will be accessed by tumor marker (AFP), CT and MRI scans

**Follow-up:** As part of standard of care, all patients will have a follow-up visit 1 month after SRT and every 3 months for 1 year and every 3 to 6 months indefinitely. The study follow-up will coincide with these visits. The last study follow-up visit will be 4 months after the completion of radiation therapy.

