## Section 1.0 Objectives

- 1.1 Primary Objective:
  - 1.1.1 The safety of hypofractionated stereotactic radiotherapy in patients with advanced hepatocellular carcinoma.
    - 1.1.1.1 Record SRT related liver, right kidney, small bowel toxicity according CTCAEv3.0
- 1.2 Secondary Objective:
  - 1.2.1 The maximum tolerable SRT dose.
  - 1.2.2 Objective tumor response rate.
    - 1.2.2.1 Report the percentage of tumor size change on CT
    - 1.2.2.2 Report the percentage of intensity change on MRI
    - 1.2.2.3 Report the percentage of change in AFP
  - 1.2.3 The value of 4D CT in liver cancer planning
    - 1.2.3.1 Report extent of liver motion three dimensionally
    - 1.2.3.2 Report the percentage of patients requiring breath gating because of the amplitude of organ motion exceeding 1 cm in any dimension.
  - 1.2.4 The value of breath gating in liver cancer SRT
    - 1.2.4.1 Report the success rate of breath gating
    - 1.2.4.2 Report the percentage of treatment time prolongation secondary to the gating.

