5.2.4 Treatment Delivery: The planning data containing the coordinates of tumor isocenter, the external infrared markers, and the implanted marker are transferred to the ExacTrac Adaptive Gating platform. The daily initial positioning will be performed using lasers and skin marks. The target isocenter will be verified on daily x-rays. If the patient meets the criteria of breath gating, treatment delivery is accomplished using the ExacTrac Adaptive Gating in combination with Novalis. External infrared markers attached to the patient's skin are used to determine the breathing pattern. The respiratory moving target is positioned, under infrared and x-ray guidance to a defined point within the patients' end expiratory breathing cycle. The gating reference level will be defined to evaluate target motion due to respiration. The size of beam-on window will be determined based on the target motion as detected by the 4D CT scan.

5.3 The study follow-up will coincide with the standard of care follow-up visits which will be 1 and 3 months after the completion of SRT. None of the tests or procedures is

performed more frequently than would be considered clinically standard. No procedures would be done exclusively for research purposes.

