#### 5.4 Toxicity:

- 5.4.1 Implantation of a liver marker: The side effects of implantation will be similar to the needle biopsy of liver tumor and the stent placement including but not limited to tumor seeding, foreign body, infection, bleeding, pain at local area, and dislocation of the marker.
- 5.4.2 SRT: Short term side effects include but not limited to skin reaction, local hair loss, fatigue, abdominal pain, nausea, vomiting, diarrhea, increasing liver function abnormality, GI bleeding or perforation which may require surgical intervention. Long term side effects are less likely to occur but if they do occur are more likely to be permanent. They include local hair loss, liver function abnormality, diarrhea, small bowel obstruction which may require surgical intervention, spinal cord injury which could result in paralysis, kidney function abnormality.

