## Appendix II

### Schedule of Activity

	Screening/Baseline	Liver Marker Implant Procedure	1-7 Days Post Implant	SRT planning,	Start SRT	End SRT	1 month Post SRT	3 Months Post SRT
History & Physical	x		x	x	x	x	x	x
CT abdomen/pelvis	x	x		x				
MRI abdomen/pelvis	x			x				x
biopsy	x							
Inclusion/Exclusion	x							
Informed consent	x							
CT or U/S guided marker implant		x						
AFP	x			x			x	x
CBC with diff	x		x	x			x	x
INR	x							
complete chemistry pannel	x		x	x			x	x
Chest X-ray or Chest CT	x							
Record adverse events		x	x	x	x	x	x	x

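### Section 10.1 scores toxicity to 1 month after SRT while adverse events are recorded to at least 3 months, and the plan does not say whether the later events enter the primary safety table

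*Combined protocol and SAP*

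**What the plan says.** The primary objective (section 1.1.1.1) is to "Record SRT related liver, right kidney, small bowel toxicity according CTCAEv3.0". It sets no time limit.

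The Endpoints part of section 10.1 contains two windows. The first is general: "Due to delayed toxicities attributable to radiotherapy", it says, "all toxicities observed within 1 month after SRT will be scored". The second belongs to the DLT definition and covers events "occurring within 30 days from the start of treatment". Section 10.4 then says that toxicity is graded and tabulated for each dose level, and gives no window.

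Data collection runs longer. In Appendix II the row "Record adverse events" is marked at every column from marker implantation to 3 months after SRT, and the chemistry panel is marked at 1 and 3 months. Section 7.1 repeats the metabolic panel at the same two visits. Section 9.3 asks for onset date, severity and relationship to treatment for every adverse event.

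On timing of harm, section 5.4.2 lists short-term and long-term effects separately and says of the latter: "Long term side effects are less likely to occur but if they do occur are more likely to be permanent". Small bowel obstruction and kidney function abnormality appear only in the long-term list.

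The end of study follow-up is given in two ways. Section 5.3 places the visits "1 and 3 months after the completion of SRT", and section 7.1 and Appendix II agree. The abstract states: "The last study follow-up visit will be 4 months after the completion of radiation therapy".

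**The concern.** The scoring sentence is not the DLT rule, which follows it with its own, differently anchored window. It therefore reads as the general window for the toxicity endpoint, and section 10.4 supplies no other. An analyst who followed it would stop the toxicity table at 1 month, although graded events with onset dates would be on file to at least 3 months.

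This bears on the primary objective. Two of the effects that the protocol itself expects in the named organs are listed only as long-term effects. The DLT list in section 10.1 has no kidney item: kidney harm counts there only if it is grade 5 or interrupts therapy for 2 weeks or more. Under that section, the toxicity table is the main route by which lesser or later kidney harm would reach the safety result.

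If the plan leaves the window open, whether late toxicity counts can be decided after the data have been seen. A reader of the final report could not tell whether an empty cell means that no late event occurred or that late events were not tabulated.

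**Working it through.** **1. The plan's own figures.** The only computed design figures are in section 10.3, for 6 evaluable patients, and they concern DLTs. With escalation if at most 1 of 6 has a DLT:
- P(not escalating) at a 35% rate = 1 − 0.65^6 − 6 × 0.35 × 0.65^5 = 68.1% (stated: at least 68%).
- P(escalating) at a 20% rate = 0.80^6 + 6 × 0.20 × 0.80^5 = 65.5% (stated: 66%).

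Both reproduce under this fixed 6-patient rule. Neither depends on the scoring window, and neither changes with the fix.

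**2. The windows side by side.**

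| Item | Place | Extent |
|---|---|---|
| Primary objective | 1.1.1.1 | no limit |
| DLT | 10.1 | 30 days from start of SRT |
| Toxicity scoring | 10.1 | 1 month after SRT |
| Toxicity table | 10.4 | none stated |
| Adverse event recording | Appendix II | to 3 months after SRT |
| Last study visit | 5.3, 7.1, Appendix II | 3 months after SRT |
| Last study visit | Abstract | 4 months after SRT |

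The two windows in 10.1 differ. SRT is 5 fractions given within 2 weeks. A 30-day window from the start therefore ends 30 − 14 = 16 days after a 2-week course, or 30 − 5 = 25 days after 5 consecutive days. The scoring window runs a full month after SRT, so it is not a restatement of the DLT window.

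**3. Share of follow-up outside the scoring window, if it is read as a limit.**
- Last visit at 3 months: (3 − 1)/3 = 67% of post-SRT follow-up.
- Last visit at 4 months: (4 − 1)/4 = 75%.
- Counting the 2-week course (about 0.5 month) as observed time: 2/3.5 = 57% and 3/4.5 = 67%.

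These are shares of time, not of events. The documents do not say how toxicity is spread over the months.

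**4. Chance that the question arises in practice.** The documents give no rate of toxicity first appearing after 1 month, so q below is an assumption, shown over a range. At the MTD there would be 16 patients: 6 from escalation (10.1) plus 10 from the expansion (10.2). Formula: P(at least one) = 1 − (1 − q)^16.

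| Assumed q | (1 − q)^16 | P(at least one late event) | Expected number, 16q |
|---|---|---|---|
| 5% | 0.440 | 56% | 0.8 |
| 10% | 0.185 | 81% | 1.6 |
| 20% | 0.028 | 97% | 3.2 |

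This takes patients as independent and all 16 as followed to the last visit. Section 5.6 removes patients for disease progression, among other reasons. Fewer patients followed would lower these chances.

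**The case against.** The strongest reply is that the plan never says that later toxicity is excluded. The scoring sentence says that all toxicities in the first month are scored, not that only those are. Its opening clause about delayed effects fits a rule meant to carry scoring past the end of treatment. Section 10.4 has no window, the primary objective has none, and section 9.3 collects severity and relationship for every event. This stands to the extent that exclusion is an inference. It does not remove the point, because no text says that later events are included either, and the one window stated in the statistical section ends at 1 month.

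A reader might also infer that kidney and small bowel toxicity as a whole is left out. The documents do not support that. Events in those organs within 1 month are scored, and section 5.4.2 lists diarrhea, gastrointestinal bleeding and perforation as short-term effects. What is at risk is the later part. Section 5.4.2 calls long-term effects less likely and gives no onset time, so the documents do not show that such effects would appear before the last visit.

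A reader might go further and infer that the MTD would be declared without regard to late events already seen in earlier cohorts. That is too strong. Section 9.3 provides for weekly review of patients on study and review at each follow-up visit. It halts escalation pending review of all data if a significant hazard appears at any time, whether or not the formal stopping rules are met. It does not name the declaration of the MTD or the opening of the expansion, but it does not leave late events unseen. Section 9.3 also treats any grade 4 or greater toxicity as a DLT without a time window. That differs from section 10.1, and the two must be reconciled, but it is a separate matter.

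Finally, the late-event rates in the working are assumed. They show when the ambiguity would matter, not how often late toxicity will occur.

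**Conclusion.** The point holds as a mismatch between the scoring window in 10.1 and the recording period in Appendix II, left unresolved by 10.4. Read as written, the rule would leave toxicity recorded after 1 month out of the primary safety table. That covers 2 of 3 post-SRT months, or 3 of 4 on the abstract's schedule. The effects most plainly affected are kidney function abnormality and small bowel obstruction.

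At assumed late-event rates of 5% to 20%, it is more likely than not that at least one of 16 fully followed patients at the MTD would have such an event. No sample size or operating characteristic is affected.

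The different last visits, 3 and 4 months, are a plain contradiction, and they set where the safety record ends. The conclusion does not rest on any claim that the plan expressly excludes late events or that safety monitoring ignores them.

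**What to change.** Leave the DLT window and the 4-week wait between dose levels as they are. State in sections 10.1 and 10.4 that all SRT-related toxicity recorded through the last study visit is graded by CTCAE v3.0 and tabulated for each dose level, split into up to 1 month and after 1 month following SRT. Make clear that this table is separate from the DLT assessment.

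Reconcile the last study visit between the abstract (4 months) and sections 5.3 and 7.1 and Appendix II (3 months), so that the end of the safety table is defined.

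The cost is a few sentences and one extra table column. No sample size or escalation rule changes, and the tabulation itself needs no added visit or test.

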## **Section 5.0 Research Design**

- 5.1 Liver marker implantation: Under CT or ultrasound guidance, a marker will be implanted into the liver tumor in a fashion similar to liver tumor biopsy and a stent placement. Prophylactic antibiotics will be given to prevent infection. The marker position and geometry will be documented on the simulation CT scan for planning SRT.
- 5.2 SRT:
  - 5.2.1 Machine: Novalis with 6 MV photons will be used for imaging guided SRT.
  - 5.2.2 Doses: Doses of 40, 50, 60 or 70 Gy (daily doses of 8, 10, 12 or 14 Gy in 2 weeks) will be prescribed to 90% isodose line. The prescription isodose volume should encompass the entire PTV. The subjects will be divided into groups of 5

to receive escalating doses of the SRT. The first group will receive a daily dose of 10Gy (Dose Level II). The next group will be enrolled only after the first group has been observed for 4 weeks following the SRT to document any side effects. The observation period will be used for every increase in dose level. Each subject will only receive one dose level of the SRT.

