#### Dose-escalation Rules

A standard cohort escalation design will be employed to evaluate 3 dose levels of SRT. Three patients will initially be treated at each dose level. A minimum of 1 month of observation after surgery is required in all 3 patients before escalation is initiated.

At the second dose level, 3 patients are entered. If:

0/3 have DLT	then the third dose level is investigated.
2/3 have DLT	then the MTD is exceeded at the second dose level. De-escalation of SRT to the first dose level will be considered.
1/3 have DLT	then 3 additional patients are entered. If none of the additional patients develop DLT, then the third dose will be investigated. Otherwise, the MTD is exceeded at the second dose level. De-escalation of SRT will be considered.

At the third dose level, 3 patients are entered. If:

0/3 have DLT	then the fourth dose level is investigated.
2/3 have DLT	then the MTD is exceeded at the third dose level. The second dose level will be expanded to a total of 6 patients (if only 3 patients had been treated).
1/3 have DLT	then 3 additional patients are entered. If none of the additional patients develop DLT, then the fourth dose will be investigated. Otherwise, the MTD is exceeded at the third dose level.

At the fourth dose level, 3 patients are entered. If:

0-1/3 have DLT	then 3 additional patients are entered. If at most 1 of 6 patients develops DLT, then the fourth dose will be declared the MTD. Otherwise, the MTD is exceeded and the third dose level will be expanded to a total of 6 patients (if only 3 patients had been treated).
2/3 have DLT	then the MTD is exceeded and the third dose level will be expanded to a total of 6 patients (if only 3 patients had been treated).

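### Section 10.1 closes the DLT window 30 days from the start of SRT, before the 4-week post-SRT wait ends, while section 9.3 defines and acts on a DLT differently and no text says which governs escalation

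*Combined protocol and SAP*

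**What the plan says.** **Window.** Section 10.1 (Endpoints) gives two periods in consecutive sentences. The first reads "Due to delayed toxicities attributable to radiotherapy, all toxicities observed within 1 month after SRT will be scored". The second limits a DLT to a listed event "that is possibly, probably or definitely related to SRT occurring within 30 days from the start of treatment".

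**Wait before escalation.** Section 5.2.2 states "The next group will be enrolled only after the first group has been observed for 4 weeks following the SRT". Section 9.3 states "There will be a four week waiting period after the last patient in each cohort completes radiation therapy for toxicity evaluation between dose levels". The escalation rules in 10.1 state "A minimum of 1 month of observation after surgery is required in all 3 patients before escalation is initiated"; the trial involves no surgery, so SRT is presumably meant.

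**Definition.** Section 10.1 lists items a to f: grade 4–5 hepatic, gastrointestinal and platelet toxicity, persistent grade 4 enzyme elevation, long treatment interruption, and related death. Section 9.3 states "Any grade 4 or greater toxicity according to CTCAE v3 will constitute a DLT", with no window, organ list or attribution, and follows this at once with a rule stopping escalation after two DLTs at a dose level.

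**Action after one DLT.** For one DLT in three patients at the second dose level, 10.1 states "then 3 additional patients are entered. If none of the additional patients develop DLT, then the third dose will be investigated". Section 9.3 calls for five more patients at the same dose.

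**Precedence.** Section 5.6.3 cites 10.1 for the DLT definition, but as a reason to take a patient off study. Nothing says whether 9.3 or 10.1 controls escalation.

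**The concern.** The DLT count decides every dose step and sets the MTD. Section 10.1 recognises that radiation toxicity can be late, yet starts its DLT clock at the first fraction, so the clock runs out while the cohort is still under mandated observation. A listed, related severe event in the last days of that observation is recorded but is not a 10.1 DLT.

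Section 9.3 would count it. It would also count related grade 4 events in organs missing from the 10.1 list, such as the kidney, as well as unrelated ones. In the other direction, 10.1 counts "any adverse event requiring interruption of therapy by" 2 weeks or more whatever its grade, which 9.3 does not. Two teams, each following the text, could make different dose decisions on the same data.

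**Working it through.** **1. Calendar.** Inputs: five daily fractions (10.1) within 2 weeks (Abstract, 5.2.2); DLT window of 30 days from the start (10.1); wait of 28 days after SRT (5.2.2, 9.3). Call the first fraction day 1 and the last day L. The window closes on day 30, the wait ends on day L + 28, and the gap is L + 28 − 30 = L − 2.

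| Last fraction | Wait ends | Gap | Wait days still inside the window |
|---|---|---|---|
| day 5 | day 33 | 3 days | 25 of 28 |
| day 7 | day 35 | 5 days | 23 of 28 |
| day 14 | day 42 | 12 days | 16 of 28 |

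If the first fraction is called day 0, each gap is one day shorter (2, 4 and 11). The 1-month post-SRT visit falls on days 33–42 if a month is 28 days after the last fraction, or 35–44 if it is 30 days. Both ranges lie wholly after day 30.

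**2. One event under both sections.** Take a related grade 4 hepatic event on day 32 in a cohort of three with no other DLT. Day 32 is outside the 10.1 window and inside the wait.
- Under 10.1 the count is 0/3, and the rule is to escalate unless the judgement-based halt in 9.3 is invoked.
- Under 9.3 it is one DLT, and more patients are treated at the same dose.

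**3. The plan's own operating figures.** Section 10.3 gives 68% (not escalating at a true DLT rate of 35%) and 66% (escalating at 20%). With six patients and escalation on at most one DLT, P(2 or more of 6) at 35% is 0.681 and P(at most 1 of 6) at 20% is 0.655, so both figures are reproduced to within a percentage point. They describe a fixed group of six, not the staged rule in the 10.1 tables. For that rule, with p the counted DLT risk and q = 1 − p:

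P(escalate) = q³ + 3pq² × q³

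- p = 0.35: 0.275 + 0.122 = 0.396, or 40%.
- p = 0.20: 0.512 + 0.197 = 0.709, or 71%.

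The staged rule is used below because it is the one that would be followed.

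**4. Illustration of the gap.** The documents give no onset distribution. Assume a 35% risk of a listed event from first fraction to end of wait, spread evenly over the days. The share f in the gap is gap ÷ (L + 28), and the counted risk is p = 0.35(1 − f).

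| Last fraction | f | p | P(escalate) |
|---|---|---|---|
| no gap | 0 | 0.350 | 0.396 |
| day 5 | 3/33 = 9% | 0.318 | 0.317 + 0.141 = 0.458 |
| day 7 | 5/35 = 14% | 0.300 | 0.343 + 0.151 = 0.494 |
| day 14 | 12/42 = 29% | 0.250 | 0.422 + 0.178 = 0.600 |

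At a 20% risk the same shares move 71% to 75%, 77% and 83%. If no events fall in the gap, nothing changes.

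**5. Five versus three.** If five means five patients added to a first cohort of three, with escalation only if none of the five has a DLT, then P(escalate) = q³ + 3pq² × q⁵. This gives 0.326 at p = 0.35 and 0.638 at p = 0.20, against 0.396 and 0.709 under 10.1. No timing assumption is needed, but the reading of five is itself an assumption.

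**The case against.** **Most of the wait is counted.** A reader might infer that severe related events during the post-SRT wait do not count under 10.1. The documents do not support that: on the day-1 count, 16 to 25 of the 28 days lie inside the window, and listed events on those days are DLTs. Only the tail is lost. Nor is a wait longer than the DLT window contradictory in itself.

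**The effect could be small.** One might suppose that half of all severe events fall in the gap, which would make the chance of escalating much higher. Nothing in the documents supports such a share. For a short course, even spread puts only 9–14% there.

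**Section 10.1 probably governs.** The escalation tables are there, and the only cross-reference to a DLT definition points there. This is a fair inference, but 5.6.3 concerns patient removal, and 9.3 attaches its own definition directly to stopping escalation. If 10.1 does govern, the window problem remains.

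**The day-32 case is not automatic escalation.** Section 9.3 requires a halt, whatever the formal rules say, if the data suggest a significant hazard, and patients are reviewed weekly. That is a real safeguard, but it rests on judgement and does not alter the DLT count that sets the MTD.

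**Blood tests may fall inside the window.** Appendix II shows the first CBC and chemistry panel after SRT at the 1-month visit. It would be too strong to conclude that none is drawn earlier: 7.1 lists an undated post-SRT panel separately from follow-up, and the hold rule in 5.5 needs counts during SRT.

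**Five may not mean three plus five.** Eight patients would exceed the 3–6 cohort size in the Abstract and 10.1. The number could mean the affected patient plus five, or be a remnant of the groups of 5 in 5.2.2. This objection stands, so step 5 is conditional.

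**Kidney toxicity need not be dose-limiting.** The primary objective is to record it, and items e and f already catch related renal events that are fatal or interrupt treatment for 2 weeks. That is fair, but 9.3 already counts other grade 4 renal events, so the two sections still disagree.

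**Conclusion.** The point holds and should be fixed before enrolment. Taken as written, the 10.1 window closes 2 to 5 days before the 4-week wait ends for a 5- to 7-day course and up to 12 days before at the 2-week maximum, and always before the 1-month visit. Sections 9.3 and 10.1 differ on what a DLT is and on how many patients follow the first one, with precedence for escalation left to inference.

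The day counts and the textual conflict rest on the documents alone. The probabilities do not: a rise from 40% to about 46–49%, or about 60% at the maximum, assumes a 35% risk and even spread, and the true effect cannot be derived. The five-versus-three comparison (33% against 40% at a 35% risk; 64% against 71% at 20%) holds only if five are added to a cohort of three. The documents do not show that the plan ignores late toxicity, which is still scored and can trigger a halt. The defect is that it may be left out of the count that sets the dose.

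**What to change.** - Keep one DLT definition, in 10.1, and have 9.3 refer to it.
- Count DLTs from the first fraction through the 1-month post-SRT visit.
- Keep items a to f and add any other SRT-related toxicity of grade 4 or above, including renal. Relying on the present list alone would drop related events that 9.3 now counts.
- Use one expansion number: three, as in the 10.1 tables. Change the groups of 5 in 5.2.2 to cohorts of 3.
- Align the waits in 5.2.2, 9.3 and 10.1, replacing the reference to surgery in 10.1 with the last SRT fraction, so that no cohort escalates until every patient's 1-month visit is complete.

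Cost: a wording amendment to 5.2.2, 9.3 and 10.1, with no new visits or tests. Slightly more events would count as DLTs than under 10.1 now, unrelated grade 4 events that 9.3 counts would no longer count, and escalation may wait a few more days. Kidney effects, which 5.4.2 lists among long-term risks, may still appear after the window.
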